 13. Willingness of men and women of reproductive potential to observe conventional and effective birth control for the duration of treatment and for 3 months following the last dose of study treatment; this may include barrier methods such as a condom or diaphragm with spermicidal gel. Male study participants should refrain from sperm donation during study treatment and up to 6 months following the last dose of selpercatinib.
 14. Written informed consent and any local required authorization (e.g., Health Insurance Portability and Accountability Act in the US, European Union [EU] Data Privacy Directive in the EU) obtained from the patient/legal representative prior to performing any protocol-related procedures, including screening evaluations.
 15. Cohorts 1 and 2: failed or intolerant to standard of care; see [Synopsis Table 2](#) for Examples.

Synopsis Table 2: Standard of Care Therapies for Cohort 1 and 2

| COHORT | THERAPY |
|--|---|
| Cohort 1: RET Fusion-Positive Solid Tumor | 
NSCLC: platinum-based chemotherapy (or other chemotherapy if not eligible for platinum) or PD-1/PD-L1 immunotherapy or both
 
Thyroid: sorafenib, patients must also be radioactive iodine-refractory as appropriate
 
Colorectal: fluoropyrimidine-based chemotherapy, with or without anti-VEGF-directed therapy or anti-EGFR-directed therapy as appropriate for the disease
 
Pancreas: fluoropyrimidine-based, gemcitabine-based, or S-1 chemotherapy
 
Breast: anthracycline, taxane, HER2-directed therapy and/or hormonal therapy or other standard therapy appropriate for the disease
 
Other: prior standard therapy for the disease
 |
| Cohort 2: RET -mutant MTC | No approved SOC |

Abbreviations: EGFR-epidermal growth factor receptor; HER2-human epidermal growth factor receptor 2; MTC-medullary thyroid cancer; NSCLC-non-small cell lung cancer; PD-1-programmed cell death protein 1; PD-L1-programmed death-ligand 1; VEGF-vascular endothelial growth factor.

16. Cohorts 1-2: enrollment will be restricted to patients with evidence of a *RET* gene alteration in tumor (i.e., not just blood) as defined in [Synopsis Table 1](#). However, a positive germline DNA test for a *RET* gene mutation as defined in Appendix B (Table 11-2) is acceptable in the absence of tumor tissue testing for patients with MTC.

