 - If archived tumor tissue was obtained prior to progression on the last MKI with anti-RET activity, the patient should undergo a fresh tumor biopsy, if it is considered safe to perform, prior to treatment (optional).
9. Adequate hematologic status, defined as:
 - Absolute neutrophil count (ANC) $\geq 1.0 \times 10^9/L$ not requiring growth factor support for at least 7 days prior to treatment, and
 - Platelet count $\geq 75 \times 10^9/L$ not requiring transfusion support for at least 7 days prior to treatment, and
 - Hemoglobin (Hb) ≥ 9 g/dL not requiring transfusion support or erythropoietin for at least 7 days prior to treatment.
 10. Adequate hepatic function, defined as:
 - Alanine aminotransferase (ALT) or aspartate aminotransferase (AST) $\leq 2.5 \times$ the upper limit of normal (ULN) or $\leq 5 \times$ ULN with documented liver involvement (such as liver metastasis or a primary biliary tumor) and
 - Total bilirubin $\leq 1.5 \times$ ULN or $\leq 3 \times$ ULN with documented liver involvement (patients with Gilbert's Disease may be enrolled with prior Sponsor approval).
 11. Adequate renal function, with estimated glomerular filtration rate ≥ 30 mL/minute. Sites can use their own clinical standard for eGFR. If no clinical standard, below MDRD study equation can be used: $eGFR (mL/min/1.73 m^2) = 175 \times (S_{cr}/88.4)^{-1.154} \times (Age)^{-0.203} \times (0.742$ if female) $\times (1.212$ if African American) (SI units).
 12. Ability to swallow capsules and comply with outpatient treatment, laboratory monitoring, and required clinic visits for the duration of study participation.
 13. Willingness of men and women of reproductive potential to observe conventional and effective birth control for the duration of treatment and for 3 months following the last dose of study treatment; this may include barrier methods such as a condom or diaphragm with spermicidal gel.

Notes:

- A postmenopausal woman will be defined as having no menses for 12 months without an alternative medical cause. Male sterility will be defined as only men sterilized surgically. For male patients with a pregnant partner, a condom should be used for contraception. For male patients with a non-pregnant female partner of child-bearing potential and woman of child-bearing potential one of the following birth control methods with a failure rate of less than 1% per year when used consistently and correctly are recommended:

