 - a. Combined estrogen and progesterone containing hormonal contraception associated with inhibition of ovulation given orally, intravaginally, or transdermally
 - b. Progesterone-only hormonal contraception associated with inhibition of ovulation given orally, by injection, or by implant

- c. Intrauterine device (IUD)
 - d. Intrauterine hormone-releasing system (IUS)
 - e. Bilateral tubal occlusion
 - f. Vasectomized partner
 - g. Sexual abstinence
 - Birth control methods unacceptable for this clinical trial are:
 - a. Periodic abstinence (calendar, symptothermal, or post-ovulation methods)
 - b. Withdrawal (coitus interruptus)
 - c. Spermicide only
 - d. Lactational amenorrhea method
 - Male study participants should refrain from sperm donation during study treatment and up to 6 months following the last dose of selpercatinib.
14. Written informed consent and any local required authorization (e.g., Health Insurance Portability and Accountability Act in the US, European Union [EU] Data Privacy Directive in the EU) obtained from the patient/legal representative prior to performing any protocol-related procedures, including screening evaluations.
15. Cohorts 1 and 2: failed or intolerant to standard of care; see [Table 4-1](#) for Examples.

Table 4-1 Standard of Care Therapies for Cohort 1 and 2

| Cohort | Therapy |
|--|---|
| Cohort 1: RET Fusion-Positive Solid Tumor | 
NSCLC: platinum-based chemotherapy (or other chemotherapy if not eligible for platinum) or PD-1/PD-L1 immunotherapy or both
 
Thyroid: sorafenib, patients must also be radioactive iodine-refractory as appropriate
 
Colorectal: fluoropyrimidine-based chemotherapy, with or without anti-VEGF-directed therapy or anti-EGFR-directed therapy as appropriate for the disease
 
Pancreas: fluoropyrimidine-based, gemcitabine-based, or S-1 chemotherapy
 
Breast: anthracycline, taxane, HER2-directed therapy and/or hormonal therapy or other standard therapy appropriate for the disease
 
Other: prior standard therapy for the disease
 |
| Cohort 2: RET -mutant MTC | No approved SOC |

Abbreviations: EGFR-epidermal growth factor receptor; HER2-human epidermal growth factor receptor 2; MTC-medullary thyroid cancer; NSCLC-non-small cell lung cancer; PD-1-programmed cell death protein 1; PD-L1-programmed death-ligand 1; VEGF-vascular endothelial growth factor.

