- k. Obtain a single pre-dose ECG during Screening and again on C1D1. If the C1D1 pre-dose QTcF > 470 msec (QTcF = QT (msec)/RR^{1/3}), where RR (msec) = $60 \times 1000/\text{BPM}$), the Sponsor should be notified prior to dosing to determine whether the patient remains eligible. On C1D8, C2D1 and thereafter, perform a single ECG at 2 hours (± 10 minutes) post-selpercatinib dosing. On C1D8 PK collection, an extra ECG should be timed prior to the PK sample being drawn. Dose patients in the visit to ensure accuracy of timing. If any ECG demonstrates QTcF 481-500 msec, perform an additional ECG at the same day, specific time judged by investigator. If any ECG demonstrates QTcF > 500 msec, repeat the ECG twice (triplicate in total) at the same day, specific time judged by investigator, and manually review to confirm accuracy. If QTcF > 500 msec is confirmed on 2/3 ECGs, hold selpercatinib and assess for alternative causes (concomitant medications, electrolyte abnormalities). Potassium should be > 4 mEq/L and $< \text{ULN}$ and magnesium and calcium should be within normal limits. selpercatinib may be resumed at one reduced dose level when QTcF has returned to baseline value, and with continued ECG monitoring as noted in the assessment schedule.
- l. Repeat only if EOT reading showed treatment-emergent abnormalities.
- m. For women of childbearing potential: Serum pregnancy test at Screening, serum or urine pregnancy test at Day 1 of every cycle (-2 days) (surgically sterilized females or those who have not experienced menses for at least 2 years are not required to be tested i.e., post-menopausal women who have not had menses within the last 12 months but have had menses within the last 24 months will be required to have a serum pregnancy test performed.). If screening testing is performed ≤ 7 days prior to C1D1, repeat testing does not need to occur on C1D1.
- n. Hemoglobin, hematocrit, RBC count, WBC count with differential (neutrophils [count and percent] and lymphocytes, monocytes, eosinophils, basophils [percent]), and platelet count). Patients found to have treatment-emergent hematologic toxicity of Grades 3 or 4 will be monitored at least weekly until resolution. If screening testing is performed ≤ 7 days prior to C1D1, repeat testing does not need to occur on C1D1.

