| CONTRACEPTIVES ^a ALLOWED DURING THE STUDY INCLUDE: |
| Highly Effective Methods^b That Have Low User Dependency |
| 
 • Implantable progestogen-only hormone contraception associated with inhibition of ovulation^c • Intrauterine device (IUD) • Intrauterine hormone-releasing system (IUS)^c • Bilateral tubal occlusion • Vasectomized partner • (Vasectomized partner is a highly effective contraceptive method provided that the partner is the sole sexual partner of the woman of childbearing potential and the absence of sperm has been confirmed. If not, an additional highly effective method of contraception should be used. Spermatogenesis cycle is approximately 90 days.) |
| Highly Effective Methods^b That Are User Dependent |
| 
 • Combined (estrogen- and progestogen-containing) hormonal contraception associated with inhibition of ovulation^c 
 ○ oral ○ intravaginal ○ transdermal ○ injectable • Progestogen-only hormone contraception associated with inhibition of ovulation^c 
 ○ oral ○ injectable • Sexual abstinence (Sexual abstinence is considered a highly effective method only if defined as refraining from heterosexual intercourse during the entire period of risk associated with the study intervention. The reliability of sexual abstinence needs to be evaluated in relation to the duration of the study and the preferred and usual lifestyle of the participant.) |
| 
a) Contraceptive use by men or women should be consistent with local regulations regarding the use of contraceptive methods for those participating in clinical studies.
 
b) Failure rate of <1% per year when used consistently and correctly. Typical use failure rates differ from those when used consistently and correctly.
 
c.) If locally required, in accordance with Clinical Trial Facilitation Group (CTFG) guidelines, acceptable contraceptive methods are limited to those which inhibit ovulation as the primary mode of action.
 
Note: Periodic abstinence (calendar, symptothermal, post-ovulation methods), withdrawal (coitus interruptus), spermicides only, and lactational amenorrhoea method (LAM) are not acceptable methods of contraception for this study. Male condom and female condom should not be used together (due to risk of failure with friction)
 |

Collection of Pregnancy Information

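### Criterion 13 lets a woman of childbearing potential qualify on a barrier method alone, although the methods that Section 4.1 recommends and Appendix I lists all fail in under 1% per year

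*Protocol*

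**What the plan says.** Three places in the protocol deal with contraceptive method.

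- **Criterion 13, Synopsis and Section 4.1.** Both versions cover men and women of reproductive potential. Both require effective birth control "for the duration of treatment and for 3 months following the last dose of study treatment" and go on to say that "this may include barrier methods such as a condom or diaphragm with spermicidal gel". Neither asks for a second method, states a failure rate or refers to Appendix I.
- **Note to criterion 13, Section 4.1 only.** For women of childbearing potential, and for male patients with a non-pregnant partner of childbearing potential, it says that "one of the following birth control methods with a failure rate of less than 1% per year when used consistently and correctly are recommended". A second list opens with "Birth control methods unacceptable for this clinical trial are" and names four methods: periodic abstinence, withdrawal, spermicide alone and lactational amenorrhea.
- **Appendix I, contraception guidance.** The table is headed contraceptives "ALLOWED DURING THE STUDY INCLUDE". Both of its blocks are labelled highly effective, with the footnote "Failure rate of <1% per year when used consistently and correctly". The note beneath it repeats the four unacceptable methods and warns against using male and female condoms together.

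Other provisions show how the sponsor regards pregnancy on study. Criterion 35 excludes pregnant and lactating women. Section 6.4 lists pregnancy as a reason to stop treatment. Appendix I says that a participant who becomes pregnant discontinues study drug or is withdrawn. Table 7-1, footnote m, sets the testing schedule for women of childbearing potential: "Serum pregnancy test at Screening, serum or urine pregnancy test at Day 1 of every cycle".

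**The concern.** Eligibility is decided on criterion 13, and on this point it is the least demanding of the three texts. The under-1% standard appears only as a recommendation in the Section 4.1 note and as guidance in Appendix I. The duration appears only in criterion 13. No sentence therefore requires a woman of childbearing potential to use an under-1% method for treatment plus 3 months.

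What is at stake is fetal exposure to study drug. Contraception is the measure that prevents it, whereas a test on Day 1 of each cycle finds a pregnancy only after conception. There is also a cost to the patient: a woman with advanced cancer who becomes pregnant comes off study drug or leaves the study. The estimate and interval for the objective response rate are not at issue.

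**Working it through.** No power, alpha or event count enters this point, and the plan gives no figure to reproduce. The check sets the texts side by side and counts the methods.

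| Text | Force | Methods named | Barrier methods among them | Failure-rate limit | Duration |
|---|---|---|---|---|---|
| Criterion 13, Synopsis | Entry requirement | Condom; diaphragm with gel (as examples) | Accepted | None | Treatment + 3 months |
| Criterion 13, Section 4.1 | Entry requirement | Same | Accepted | None | Treatment + 3 months |
| Note to criterion 13, Section 4.1 | Recommendation | 7 | 0 | Under 1% per year | None of its own |
| Appendix I table | Guidance, non-exclusive heading | 8 | 0 | Under 1% per year | None beyond the study |
| Unacceptable lists, Section 4.1 and Appendix I | Prohibition | 4 in each, the same four | 0 | Not applicable | Not applicable |

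**Counts.** The Section 4.1 note has seven items: combined hormonal, progestogen-only, IUD, hormone-releasing IUS, tubal occlusion, vasectomized partner and abstinence. Appendix I has five methods of low user dependency (progestogen implant, IUD, IUS, tubal occlusion, vasectomized partner) and three user-dependent ones (combined hormonal, progestogen-only, abstinence), so 5 + 3 = 8. Appendix I separates the implant from the other progestogen-only forms, which accounts for the difference: 7 + 1 = 8. Among the forms listed, the one Appendix I option that the note lacks is injectable combined hormonal contraception.

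**Applying the text to one candidate.** Take a woman of childbearing potential who uses only a diaphragm with spermicidal gel.

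1. Criterion 13 covers her, because it names women, and it gives her method as an example of what is acceptable.
2. The unacceptable lists do not exclude her. They bar spermicide used alone, and she uses it with a diaphragm.
3. The note does not exclude her, because it recommends.
4. The Appendix I table does not exclude her. Its heading is not exclusive, and criterion 13 does not refer to it. Section 8.2.3.4 cites Appendix I for pregnancy procedures and testing, not for permitted methods.
5. She therefore meets the criterion with a method that is on neither under-1% list.

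That a barrier method alone is enough is inferred from the absence of any second-method requirement, but it is the plain reading. Nor can the sentence be read as meant for men only: it names women, and a diaphragm is a female method.

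**The case against.** The strongest reply is that the texts are compatible. Criterion 13 sets a minimum, the note recommends something better, and Appendix I gives guidance under a heading that does not claim to be complete. Section 4.1 repeats the Synopsis sentence, so the Synopsis is no looser than the operative criterion, and leaving the notes out of a synopsis is ordinary abridgement. All of that stands. A reader might infer that Appendix I forbids what criterion 13 allows. The documents do not support that: barrier methods are on neither unacceptable list, and the Appendix I warning about two condoms together takes condom use for granted. But compatibility does not answer the point. Because the stricter texts do not bind, the looser one governs.

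A second reply is that the need for a mandatory under-1% method is not shown. The documents give no barrier failure rate and no fetal-toxicity data, and they refer risk information to the Investigator's Brochure. Appendix I also defers to local regulations, which may be stricter. This limits what can be claimed about size. It does not explain why the sponsor's own list is not the requirement.

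A third is that other safeguards exist: a serum test at screening, a test each cycle, investigator review of menstrual history and recent sexual activity, and a ban on the four unacceptable methods. These are real, but they screen, detect or rule out other methods. They do not raise the standard of the method used.

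A reader might also infer a wider gap in pregnancy follow-up after the last dose, because Section 8.2.3.4 collects pregnancy details only until the safety follow-up visit. The documents do not support that as stated. Section 8.2.3 requires any pregnancy to be reported through the serious adverse event process. Appendix I collects information on any participant who becomes pregnant while in the study, and Section 3.3 makes long-term follow-up part of the study. At most, the sections differ in wording. In any case, changing the permitted methods would not alter the testing or reporting schedule.

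**Conclusion.** The point holds as a mismatch in strength. Both statements of criterion 13 accept a barrier method alone for women of childbearing potential, while barrier methods are 0 of the 7 methods the sponsor recommends and 0 of the 8 it lists in Appendix I. Calling the criterion looser rests on the protocol's own under-1% lists, not on an outside failure rate.

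The size in pregnancies cannot be stated. The documents give no number of women of childbearing potential, no barrier failure rate and no fetal-toxicity data. The response-rate analysis is untouched. This is an inexpensive patient-safety improvement that the sponsor should make. It is not a flaw that puts the trial's conclusions in doubt.

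**What to change.** 1. In criterion 13, in both the Synopsis and Section 4.1, require women of childbearing potential to use a method from the Appendix I highly effective list during treatment and for 3 months after the last dose. Allow a condom or diaphragm only in addition, and cross-reference Appendix I.
2. In the Section 4.1 note, make the under-1% methods required, not recommended, for these women. The present sentence covers women and male patients together, so it needs to be split.
3. Add injectable combined hormonal contraception to the note, so that it matches Appendix I.
4. Leave the provisions for men unchanged: a condom remains acceptable, including with a pregnant partner, and a highly effective method stays recommended when the partner is not pregnant and is of childbearing potential.

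The cost is an amendment and matching consent wording. Section 10.2 already requires re-consent to the current form, so a revised form could also reach women on treatment. A few women who use only a barrier method would have to change. An IUD, IUS, implant or tubal occlusion involves a procedure. Oral, intravaginal or transdermal hormonal methods, a vasectomized partner or abstinence involve none for the patient.

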| Appendix J | European Organization for Research and Treatment of Cancer (EORTC) Quality of Life Questionnaire-Core 30 (QLQ-C30) and Bowel Diary | 112 |
| Appendix K | Protocol Amendment History | 113 |

List of Abbreviations and Definition of Terms

| Abbreviation or Term | Definition |
|----------------------|--|
| AE | adverse event |
| ACTH | adrenocorticotrophic hormone |
| ALK | anaplastic lymphoma kinase |
| ALP | alkaline phosphatase |
| ALT | alanine aminotransferase |
| ANC | absolute neutrophil count |
| anti-PD1 | anti-programmed cell death protein 1 |
| AST | aspartate aminotransferase |
| ATP | adenosine triphosphate |
| AUC | area under the concentration vs time curve |
| AUC _{0-∞} | area under the concentration versus time curve from time 0 extrapolated to infinity |
| AUC _{0-t} | area under the concentration versus time curve from time 0 to t |
| AUC ₀₋₂₄ | area under the concentration versus time curve from time 0 to 24 hours |
| AUC _{tau} | area under the concentration versus time curve calculated during the dosing interval at steady state |
| BID | twice daily |
| BUN | blood urea nitrogen |
| BSA | body surface area |
| C | Cycle |
| C1D1 | Cycle 1 Day 1 |
| CAP | College of American Pathologists |
| CBR | clinical benefit rate |
| CDMS | Clinical Data Management System |
| CEA | carcinoembryonic antigen |
| cfDNA | circulating free deoxyribonucleic acid |
| CI | confidence interval |
| CL/F | apparent oral clearance of drug |
| C _{max} | maximum drug concentration |
| C _{min} | minimum drug concentration |
| CNAS | China National Accreditation Service for Conformity Assessment |
| CNS | central nervous system |
| CR | complete response |
| CT | computerized tomography |
| CTCAE | Common Terminology Criteria for Adverse Events |

| Abbreviation or Term | Definition |
|-----------------------------|--|
| CYP | cytochrome P450 |
| D | Day |
| DLT | dose-limiting toxicity |
| DNA | deoxyribonucleic acid |
| DOR | duration of response |
| ECG | electrocardiogram |
| ECOG | Eastern Cooperative Oncology Group |
| eCRF | electronic case report form |
| EDC | electronic data capture |
| eGFR | estimated glomerular filtration rate |
| EGFR | epidermal growth factor receptor |
| EORTC | European Organization for Research and Treatment of Cancer |
| EORTC QLQ-C30 | European Organization for Research and Treatment of Cancer Quality of Life Questionnaire-Core 30 |
| EOT | end of treatment |
| ER | estrogen receptor |
| FAS | Full Analysis Set |
| FGFR | fibroblast growth factor receptor |
| FISH | Fluorescence in Situ Hybridization |
| FLAIR/T2 | T2-weighted fluid-attenuated inversion recovery |
| GALT | gastrointestinal associated lymphoid tissues |
| GCP | Good Clinical Practices |
| GI | gastrointestinal |
| GLP | Good Laboratory Practice |
| GnRH | gonadotropin-releasing hormone |
| 5-HT3 | serotonin type 3 |
| H2 | histamine-2 |
| Hb | Hemoglobin |
| hERG | Human ether-à-go-go related gene |
| HRQoL | Health-Related Quality of Life |
| IB | Investigator's Brochure |
| IC ₅₀ | 50% inhibitory concentration |
| ICF | informed consent form |
| ICH | International Conference on Harmonisation |
| ICH GCP | International Conference on Harmonisation-Good Clinical Practices |

| Abbreviation or Term | Definition |
|-----------------------------|--|
| IEC | Independent Ethics Committee |
| IRB | Institutional Review Board |
| IRC | independent review committee |
| ISO/IEC | International Organization for Standardization/ Independent Ethics Committee |
| IUD | intrauterine device |
| IUS | intrauterine hormone-releasing system |
| IV | Intravenous |
| KRAS | Kirsten rat sarcoma virus oncogene |
| LDH | lactate dehydrogenase |
| LFTs | liver function tests |
| LHRH | luteinizing hormone-releasing hormone |
| LOXO-292 | investigational product (selpercatinib) |
| LTFU | Long-term Follow-up |
| MedDRA | Medical Dictionary for Regulatory Activities |
| mg | Milligram |
| MHC-I | Major Histocompatibility Complex class I |
| MKIs | multikinase inhibitors |
| MRI | magnetic resonance imaging |
| MTC | medullary thyroid cancer |
| NCI | National Cancer Institute |
| NCI CTCAE | National Cancer Institute Common Terminology Criteria for Adverse Events |
| NGS | next-generation sequencing |
| NSCLC | non-small cell lung cancer |
| ORR | objective response rate |
| OS | overall survival |
| PCR | polymerase chain reaction |
| PD | progressive disease |
| PD ₁ | initial progressive disease |
| PD ₂ | subsequent progressive disease |
| PD-1 | programmed cell death protein 1 |
| PD-L1 | programmed death-ligand 1 |
| PedsQL | Pediatric Quality of Life Inventory-Core Module |
| PET | positron emission tomography |
| PFS | progression-free survival |
| P-gp | p-glycoprotein |
| PK | pharmacokinetic |

| Abbreviation or Term | Definition |
|-----------------------------|---|
| PO | per os (oral) |
| PopPK | population pharmacokinetic |
| PP | Per-protocol Analysis Set |
| PPI | proton pump inhibitors |
| PR | partial response |
| PRO | patient-reported outcomes |
| PTC | papillary thyroid cancer |
| QD | once daily |
| QTcF | QT interval corrected for heart rate (Fridericia's formula) |
| QTcI | individual animal heart rate corrected QT intervals |
| RBC | red blood cell(s) |
| REB | Research Ethics Board |
| RECIST | Response Evaluation Criteria in Solid Tumors |
| RP2D | recommended Phase 2 dose |
| RTK | receptor tyrosine kinase |
| SAD | short axis diameter |
| SAE | serious adverse event |
| SAP | statistical analysis plan |
| SD | stable disease |
| SERDs | selective estrogen receptor degraders |
| SERMs | selective estrogen receptor modulators |
| SFU | safety follow-up |
| SOC | system organ class |
| SOD | sum of the diameters |
| SRC | Safety Review Committee |
| SRS | stereotactic radiosurgery |
| SUSARs | suspected unexpected serious adverse reactions |
| T _{1/2} | terminal elimination half-life |
| FT ₃ | Free triiodothyronine |
| FT ₄ | Free thyroxine |
| TBD | to be determined |
| TBL | total bilirubin level |
| TEAE | treatment-emergent adverse event |
| TKIs | tyrosine kinase inhibitors |
| T _{max} | time to maximum plasma concentration |
| TSH | thyroid stimulating hormone |

| Abbreviation or Term | Definition |
|---------------------------------|---------------------------------|
| ULN | upper limit of normal |
| US | United States |
| V_z/F | apparent volume of distribution |
| WBC | white blood cell |
| WBRT | whole brain radiation therapy |

1 Introduction

